8.3.1 AE Follow up

All AEs occurring during the study are to be followed up in accordance with good medical practice until they are resolved, stabilized or judged no longer clinically significant or, if a chronic condition, until fully characterized. Any AEs that are considered drug-related (possibly related, definitely related) must be followed for 30 days, or to resolution, or until no improvement is expected, whichever occurs first.

8.3.2 Overdose

No information on treatment of overdose of Ampion is currently available. In the case of overdose the patient should be followed as for an AE and appropriate supportive medical treatment instigated.

8.4 Serious Adverse Event Reporting

8.4.1 Reporting Requirements

Unexpected serious suspected adverse reactions are subject to expedited reporting to FDA. All SAEs must be entered into the eCRF within 24 hours of first knowledge of the event by study personnel. The investigator must provide his/her assessment of the relationship to study drug at the time of the initial report. The entry of an SAE into the eCRF triggers an automatic alert to the clinical research organization (CRO) safety team. The following information must be reported:

- Protocol number
- Site and/or Investigator number
- Patient number
- Demographic data
- Brief description of the event
- Onset date and time
- Resolution date and time, if the event resolved
- Current status, if event not yet resolved
- Any concomitant treatment and medication
- Investigator's assessment of whether the SAE was related to Investigative product or not.

The CRO Safety Associate will contact the site for clarification of data entered onto the eCRF, or to obtain missing information. In the event of questions regarding SAE reporting, the site may contact the appropriate individual as in [Section 8.4.2](#).

8.4.2 SAE Contact Information

Ampio Pharmaceuticals Inc, or their designee CRO, is responsible for submitting reports of AEs associated with the use of the drug that are both serious and unexpected to FDA according to 21 CFR 312.32 and the final guidance (2012). All investigators participating in ongoing clinical studies with the study medication will receive copies of these reports for prompt submission to their Institutional Review Board (IRB) or Ethics committee (EC).

9 STATISTICAL METHODS

9.1 General Considerations

This section describes the rules and conventions to be used in the presentation and analysis of the data.

This is a Phase 1 study and is not intended to be powered for the primary endpoint. The study will evaluate safety, tolerability, and efficacy of Ampion in improving the clinical course and outcome of adults with prolonged respiratory complications after a COVID-19 infection.

9.2 Analysis Populations

9.2.1 Safety Analysis Population:

The safety analysis population is defined as all patients who are randomized. Participants will be analyzed as treated.

9.2.2 Intent-to-treat Population:

The intent-to-treat (ITT) analysis population is defined as all randomized patients. All efficacy analyses will be performed in the ITT population. Patients will be analyzed as randomized.

9.2.3 Interim Analysis

An interim analysis for safety and efficacy endpoints will be performed once all subjects have completed their Day 7 assessments.

9.3 Data presentation

9.3.1.1 Demographic and Baseline Characteristics:

Demographic (e.g., age, sex, race, ethnicity) and baseline characteristics (e.g., weight, height, comorbidities) summarized using descriptive statistics, overall and by treatment group for the ITT analysis population.

9.3.1.2 Medical History and Physical Examination:

The number and percent of participants with past and current medical disorders at the time of randomization will be presented overall and by treatment group for the ITT analysis population.

9.3.1.3 Concomitant Medications or Treatments:

The number and percent of subjects receiving concomitant medications or therapies prior to and during the study and at the final visit will be tabulated and presented overall and by treatment group for the ITT analysis population.

Concomitant medications/treatments will be summarized using descriptive statistics and will be presented by type of drug (WHO DRUG classification) overall and by treatment group for the

safety and ITT analysis populations. There should be no significant differences in the use of concomitant treatments between groups. All concomitant therapies will be recorded to be able to compare any inadvertent imbalances between the groups.

9.3.1.4 Safety Data:

Safety data will be presented by treatment arm. Safety data will be evaluated by changes in the frequency and severity of AEs. Concomitant medication will be recorded for safety. AEs will be collected from baseline to Day 60. The severity of AEs (mild, moderate, severe), relatedness (related, possibly related, unrelated) along with the duration, action taken, and outcome (e.g., study withdrawal) will also be recorded.

All data collected under this study protocol will be included in the assessment of patient safety. Missing or incomplete AE data will assume greatest relationship to study drug and/or severity.

Remaining safety data will be collected from enrollment until study exit (or death). Safety data will be tabulated and presented overall and by treatment group for the safety analysis population.

9.3.1.5 Efficacy Data:

The efficacy of treatment on the clinical course and outcome of COVID-19 will be evaluated by treatment arm. Summaries will be performed by treatment arm (active or control).

Unless otherwise specified, continuous variables will be summarized with the number of non-missing observations, mean, standard deviation, median, minimum, maximum, and 95% confidence intervals displayed. Categorical data will be summarized as counts, percentages, and 95% confidence intervals.

9.4 Study Endpoints

9.4.1 Primary Endpoint

Adverse events (AEs) will be evaluated from baseline through Day 60. The primary endpoint is incidence and severity of adverse events (AEs) and serious adverse events (SAEs) from baseline to Day 28.

There will be no statistical tests for incidence and severity of AEs. AEs will be tabulated using descriptive statistics and shift tables and presented for safety.

9.4.2 Exploratory Endpoints

Exploratory efficacy endpoints assess the effect of inhaled Ampion compared to placebo on the clinical outcomes for participants with prolonged respiratory complications after a COVID-19 infection per [Section 3.3.2](#).

The efficacy endpoints will be evaluated to estimate the treatment effect and use descriptive statistics including mean, standard deviation, percentages, minimum/maximum, and 95% confidence intervals. All endpoints will be tabulated and presented by treatment arm, cohort

(moderate and severe), and timepoint. Where appropriate, data will be tabulated and presented cumulatively across cohorts and/or timepoints.

9.5 Missing and Spurious Data

All data collected under this study protocol will be included in the assessment of patient safety. Missing or incomplete AE data will assume greatest relationship to study drug and/or severity.

10 REGULATORY, ETHICAL AND LEGAL OBLIGATIONS

10.1 Declaration of Helsinki

The Principal Investigator will ensure that this Study is conducted in accordance with the most recent revision of the Declaration of Helsinki.

10.2 Good Clinical Practice

The Study will be conducted according to the study protocol and to Standard Operating Procedures (SOPs) that meet the guidelines provided by the International Conference on Harmonization (ICH) for Good Clinical Practice in clinical studies.

10.3 Institutional Review Boards/Ethics Committees

Before implementing this study, the protocol, the proposed patient informed consent forms and other information for the patients must be reviewed by a properly constituted committee or committees responsible for approving clinical studies. The IRB/IEC written signed approval letter/form must contain approval of the designated investigator, the protocol (identifying protocol title, date, and version number), and of the patient informed consent form (date, version).

Any change or addition to the protocol can only be made in a written protocol amendment that must be approved by the Sponsor, the IRB/IEC, and the Health Authorities.

10.4 Regulatory Authority Approval

Before this study is implemented, the protocol must be approved by the relevant regulatory authority.

10.5 Informed Consent

The investigator must fully inform the patient or patient's legally authorized representative of all pertinent aspects of the trial including the written information approved/favorably assessed by the IRB/IEC.

Prior to the start of the pre-study examination, the written informed consent form must be signed and personally dated by the patient and by the physician who conducted the informed consent discussion. One copy of the written information and signed consent form must be given to each patient, and one (1) copy must be retained in the investigator's study records.

10.6 Patient Confidentiality and Disclosure

Data on patients collected on eCRFs during the trial will be documented in an anonymous fashion and the patient will only be identified by the patient number, and by his/her initials. If, as an exception, it is necessary for safety or regulatory reasons to identify the patient, all parties are bound to keep this information confidential.

The investigator will guarantee that all persons involved will respect the confidentiality of any information concerning the trial patients. All parties involved in the study will maintain strict confidentiality to assure that neither the person nor the family privacy of a patient participating in the trial is violated. Likewise, the appropriate measures shall be taken to prevent access of non-authorized persons to the trial data.

10.7 Collection, Monitoring and Auditing Study Documentation, and Data Storage

10.7.1 Collection of Data and Monitoring Procedures

This study will use a 21 CFR Part 11 compliant electronic data capture system (EDC). An electronic case report form (eCRF) is used for data recording. All data requested on the eCRF must be entered and all missing data must be accounted for.

The data will be checked for completeness and correctness as it is entered by the real-time online checks applied by the EDC system. Off-line checks will also be run to perform any additional data review required. Discrepancy reports will be generated accordingly and transferred to the study center for resolution by the investigator or his/her designee.

Accurate and reliable data collection will be assured by verification and cross-check of the eCRF against the investigator's records by the study monitor (source document verification), and the maintenance of a study drug-dispensing log by the investigator.

Before study initiation, at a site initiation visit or at an investigator's meeting, a Sponsor representative will review the protocol and case report forms with the investigators and their staff. During the study a monitor will visit the site regularly to check the completeness of patient records, the accuracy of entries on the case report forms, the adherence to the protocol and to Good Clinical Practice, the progress of enrollment. The monitor will ensure during on-site visits that study medication is being stored, dispensed and accounted for according to specifications. Key trial personnel must be available to assist the monitors during these visits.

The investigator must give the monitor access to relevant hospital or clinical records, to confirm their consistency with the case report form entries. No information in these records about the identity of the patients will leave the study center. Monitoring standards require full verification for the presence of informed consent, adherence to the inclusion/exclusion criteria, documentation of SAEs and the recording of primary efficacy and safety variables. Additional checks of the consistency of the source data with the eCRFs are performed according to the study-specific monitoring plan.

10.7.2 Auditing Procedure

In addition to the routine monitoring procedures, the Sponsor or the regulatory authority can conduct an audit or an inspection (during the study or after its completion) to evaluate compliance with the protocol and the principles of Good Clinical Practice.

The investigator agrees that representatives of the Sponsor and Regulatory Authorities will have direct access, both during and after the course of this study, to audit and review all study-relevant medical records.

10.7.3 Retention of Documents

The investigator must maintain source documents for each patient in the study, consisting of all demographic and medical information, including laboratory data, and keep a copy of the signed informed consent form. All information on case report forms must be traceable to these source documents in the patient's file. Data without a written or electronic record will be defined before trial start and will be recorded directly on the case report forms, which will be documented as being the source data.

10.8 Disclosure of Information

All information provided to the investigator by Ampio Pharmaceuticals, Inc. or their designee, will be kept strictly confidential. No disclosure shall be made except in accordance with a right of publication granted to the investigator.

No information about this study or its progress will be provided to anyone not involved in the study other than to Ampio Pharmaceuticals, Inc or its authorized representatives, or in confidence to the IRB, or similar committee, except if required by law.

10.9 Discontinuation of the Study

Ampio Pharmaceuticals, Inc., may terminate the study at any time upon immediate notice from the Sponsor to all investigators for any reason, including the Sponsor's belief that discontinuation of the study is necessary for the safety of patients.

10.10 Study Report, Publication Policy and Archiving of Study Documentation

10.10.1 Study Report and Publication Policy

Depending on the outcome of the study, an ICH-compliant integrated clinical and statistical report may be prepared upon completion of the study and data analysis. The results of the study may also be published in a relevant peer-reviewed journal, with authorship status and ranking designated according to the acknowledged contributions of participating investigators, institutions and the Sponsor.

10.10.2 Study Documents

The investigator must maintain source documents for each patient in the study, consisting of all demographic and medical information, questionnaires, including laboratory data, etc., and keep a copy of the signed informed consent form. All information on the e-case report forms must be traceable to these source documents in the patient's file. Data without a written or electronic record will be defined before trial start and will be recorded directly on the e-case report forms, which will be documented as being the source data.

10.10.3 Archiving of Documents

Essential documents, as listed below, must be retained by the investigator for as long as needed to comply with national and international regulations. The Sponsor will notify the investigator(s)/institution(s) when the study-related records are no longer required. The investigator agrees to adhere to the document retention procedures by signing the protocol. Essential documents include:

- IRB/IEC/REB approvals for the study protocol and all amendments
- All source documents and laboratory records
- CRF copies (electronic copies on a CDROM)
- Patients' informed consent forms (with study number and title of trial)
- FDA form 1572
- Any other pertinent study document.

1 LIST OF ABBREVIATIONS AND DEFINITIONS OF TERMS

Abbreviation	Definition
6MWT	Six-minute walk test
AE	Adverse event
ARDS	Acute respiratory distress syndrome
BP	Blood pressure
CDC	Centers for Disease Control and Prevention
COPD	Chronic obstructive pulmonary disease
COVID-19	Coronavirus disease 19
CRO	Contract research organization
DSMB	Data and safety monitoring board
EC	Ethics committee
ECMO	Extracorporeal membrane oxygenation
eCRF	Electronic case report form
EDC	Electronic data capture
HSA	Human serum albumin
ICH	International conference on harmonization
IRB	Investigational review board
ITT	Intent to treat
IV	Intravenous
mBDS	Modified Borg Dyspnoea Scale
PASC	Post Acute Sequelae SARS-CoV-2
SAE	Serious adverse event
SOP	Standard operating procedure
Sp02	Blood oxygen saturation
TNF α	Tumor necrosis factor alpha
WHO	World Health Organization

2 INTRODUCTION

This statistical analysis plan (SAP) outlines the proposed statistical methods to be implemented during the review of data to ensure that it confirms with categories determined by the CRF or the anticipated ranges for continuous variables and analysis of data collected within the scope of Clinical Protocol AP-018, “A Randomized, Double-Blinded, Placebo-Controlled Phase I Study to Evaluate the Safety and Efficacy of Ampion in Patients with Prolonged Respiratory Symptoms due to COVID-19 (Long-COVID)”.

It is not intended that each table, listing, or graph will be included in the clinical study report (CSR). It is also possible that additional analyses will be conducted after review of the data. Any analyses or summaries not specified in the SAP, but performed after review of the data, will be identified in the CSR as post hoc.

There will be an unblinded team responsible for obtaining the required material for the analysis from the study’s unblinded data manager (DM) for the clinical trial. The unblinded team will present the results of the interim analysis at D28 to the sponsor in a blinded fashion.

2.1 PURPOSE OF THE ANALYSES

The severe acute respiratory syndrome coronavirus 2 (SARS-CoV-2) has resulted in the pandemic spread of coronavirus disease 2019 (COVID-19), which has a high rate of infection, has a high rate of hospitalization, and has overwhelmed healthcare systems. Increasing numbers of people with COVID-19 are experiencing the lingering effects of COVID-19 and continue to have prolonged respiratory complications months after the onset of the disease, also known as Post-Acute Sequelae of SARS-CoV-2 (PASC), long-COVID, and/or long-hauler patients.

The SARS-CoV-2 virus is transmitted through the respiratory system, which can cause a severe dysregulation of the immune response and damage in the lungs. Chronic, prolonged inflammation of the lungs maybe responsible for a myriad of continuing respiratory signs and symptoms post-infection, including cough, shortness of breath, chest discomfort, low exercise tolerance and low blood oxygen saturation.

Ampion is the low molecular weight filtrate of human serum albumin with the in vitro ability to modulate inflammatory cytokine levels. Ampion has the potential to improve clinical outcomes for long-COVID patients.

This study aims to evaluate the safety of Ampion and the clinical outcomes in patients with long-COVID. This is the first study for at-home use of Ampion inhaled treatment for long-COVID patients and will be used to inform decisions for the clinical development of Ampion.

2.2 STUDY OBJECTIVES

2.2.1 Primary Objective

The primary trial objective is to evaluate the safety and tolerability of inhaled Ampion versus placebo control in adult participants with prolonged respiratory complications after COVID-19 infection.

2.2.2 Secondary Objective

The exploratory trial objectives evaluate the efficacy of inhaled Ampion versus placebo control in improving the clinical course and outcomes of participants with prolonged respiratory complications after a COVID-19 infection.

2.3 ENDPOINTS

2.3.1 Primary

Adverse events (AEs) will be evaluated from baseline through Day 60. The primary endpoint is incidence and severity of adverse events (AEs) and serious adverse events (SAEs) from baseline to Day 28 and Day 60.

2.3.2 Exploratory

Exploratory efficacy endpoints assess the effect of inhaled Ampion compared to placebo on the clinical outcomes for participants with prolonged respiratory complications after a COVID-19 infection as follows:

Objective	Endpoint
Assess the effect of Ampion compared to placebo on symptom improvement	
• Change in FDA Assessment of 14 Common COVID-19-Related Symptoms questionnaire from baseline to Day 7; Day 28; Day 60• Change in Borg Dyspnoea Scale (mBDS) from baseline to Day 7; Day 28; Day 60• Change in all-cause mortality
Assess the effect of Ampion compared to placebo on pulmonary function	
• Change in blood oxygen saturation from baseline to Day 7; Day 28; Day 60• Change in six-minute walk test (6MWT) score from baseline to Day 7; Day 28; Day 60
Assess the effect of Ampion compared to placebo on global impression	
• Change in Quality-of-Life Assessment using SF-36 from baseline to Day 7; Day 28; Day 60

	
• Change in Fatigue questionnaire from baseline to Day 7; Day 28; Day 60• Change in Sleep Disturbance questionnaire from baseline to Day 7; Day 28; Day 60
Assess the effect of Ampion compared to placebo on radiographic findings	
• Change in chest imaging on ground-glass opacity, local patchy shadowing, bilateral patchy shadowing, and/or interictal abnormalities from baseline to Day 60

3 STUDY METHODS

3.1 STUDY DESIGN

This is a randomized, double-blinded, placebo-controlled Phase I trial to evaluate the safety and efficacy of a 5-day Ampion inhalation treatment in participants with prolonged respiratory complications after a COVID-19 infection.

Participants with COVID-19 infection will be screened for eligibility and consented. Participants (n=30) will be randomized in one of two groups, active (n=15) or placebo control (n=15) and randomized 1:1 following an equal allocation. The treatment arm will receive Ampion inhalation treatment, and the control arms will receive saline inhalation treatment. Participants will be followed for 60 days.

3.2 RANDOMIZATION AND BLINDING

The treatment in this study will be blinded to the subjects, investigators, any individual conducting the study (e.g., nursing and pharmacy staff) and clinical study personnel. Participants will be assigned to treatment by a randomization schedule developed and maintained by an independent statistician.

Participants are randomized 1:1 to active treatment or placebo control, following an equal allocation to treatment arms as follows:

Treatment Arm	Investigational Treatment
Active	Ampion Inhalation for 5-days
Control	Placebo Inhalation for 5-days

Given the changing nature of the pandemic, periodic adjustments to the allocation ratio may be made in an effort to achieve equal allocation across the treatment arms at the end of the enrollment.

Study drug and placebo will be provided as blinded investigational product (IP) with appropriate labeling to link to the randomization code. Where required, safety personnel and/or investigator may be unblinded to a particular subject's treatment assignment to meet reporting requirements to Regulators.

A data management plan and statistical analysis plan will be approved by the sponsor prior to unblinding study data.

4 SAMPLE SIZE

This is a Phase I study and is not intended to be powered for the primary endpoint. This trial is designed to enroll up to 30 subjects, randomized to active treatment or placebo control, following an equal allocation to treatment arms (n=15 subjects per arm).

5 STUDY ENDPOINTS AND ANALYSES

5.1 PRIMARY ENDPOINT

The primary endpoint is incidence and severity of adverse events (AEs) and serious adverse events (SAEs) from baseline to Day 28.

The hypotheses to be tested are:

$$H_0: \pi_A = \pi_S \text{ versus } H_A: \pi_A \neq \pi_S$$

Where π_A and π_S represent the adverse event rates for Ampion and placebo during the first 28 days after randomization.

The difference between Ampion and Placebo will be tested using the appropriate chi-square test or Fisher's exact test utilizing PROC FREQ with the EXACT option, if necessary.

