5.2 EXPLORATORY (EFFICACY) ENDPOINTS

There are several exploratory endpoints. In order to preserve the alpha level these will be tested hierarchically in the order presented here. Each endpoint along with the analysis method and SAS procedure to analyze the data is presented.

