8.2 ADVERSE EVENTS

Adverse events (AEs) will be evaluated from baseline through Day 60. The primary endpoint is incidence and severity of adverse events (AEs) and serious adverse events (SAEs) from baseline to Day 28. The primary endpoint analysis is presented in Section 5.1.

There will be no statistical tests for incidence and severity of AEs. AEs will be tabulated using descriptive statistics and shift tables of lab tests will be presented for safety assessment.

All reported AEs, will be listed, documenting the course, outcome, severity, and causality to study drug. Verbatim terms on CRFs will be mapped to preferred terms and related system organ class using the Medical Dictionary for Regulatory Activities (MedDRA).

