10.3 Safety

10.3.1	Exposure to Study Treatment
10.3.2	Incidence and Severity of Treatment-Emergent (TEAE) Events from Baseline to Day 28
10.3.3	Incidence and Severity of Serious Treatment-Emergent (TEAE) Events from Baseline to Day 28
10.3.4	Overall Summary of Treatment-Emergent Adverse (TEAE) Events
10.3.5	Incidence of TEAEs by System Organ Class and Preferred Term
10.3.6	Incidence of Treatment-Emergent Related AEs by System Organ Class and Preferred Term
10.3.7	Incidence of Treatment-Emergent Serious Adverse Events (SAEs) by System Organ Class and Preferred Term
10.3.8	Incidence of TEAEs by Preferred Term in Descending Order of Frequency

10.3.9	Incidence of Treatment-Emergent Related AEs by Preferred Term in Descending Order of Frequency
10.3.10.1	Summary of Pulse Change from Baseline over Time (bpm)
10.3.10.2	Summary of Body Temperature and Change from Baseline over Time (F)
10.3.10.3	Summary of Systolic BP and Change from Baseline over Time (mmHg)
10.3.10.4	Summary of Diastolic BP and Change from Baseline over Time (mmHg)
10.3.10.5	Summary of Respiration Rate and Change from Baseline over Time
10.3.11.1	Concomitant Medication Use by ATC Level 1
10.3.11.2	Concomitant Medications Preferred Term in Descending Order of Use
10.3.11.3	Medication Started on Study Preferred Term in Descending Order of Use

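### The only hypothesis test specified for the primary safety endpoint ignores severity and SAEs, and SAP 8.2 and Protocol 9.4.1 say AEs will not be tested at all

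*SAP*

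**What the plan says.** SAP 5.1 defines the endpoint in two dimensions and for two classes of event: "The primary endpoint is incidence and severity of adverse events (AEs) and serious adverse events (SAEs) from baseline to Day 28". Protocol 9.4.1 defines it in the same way.

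SAP 5.1 then sets one null hypothesis, equality of two proportions that "represent the adverse event rates for Ampion and placebo during the first 28 days after randomization", and one method: "The difference between Ampion and Placebo will be tested using the appropriate chi-square test or" Fisher's exact test. It does not say whether the rate counts participants or events, or all AEs or only treatment-emergent ones.

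SAP 8.2 refers the reader to Section 5.1 for the primary endpoint analysis. Its next paragraph begins: "There will be no statistical tests for incidence and severity of AEs". Protocol 9.4.1 says the same.

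Severity and seriousness are handled descriptively. SAP 8 plans AE summaries by arm, broken down by AE or SAE, severity and relationship. Table 10.3.2 is titled "Incidence and Severity of Treatment-Emergent (TEAE) Events from Baseline to Day 28", and Table 10.3.3 is its counterpart for serious events. Under SAP 7, categorical variables get counts and percentages, and a confidence interval is promised only for change from baseline. No between-arm difference or interval is therefore specified for severe AEs or SAEs.

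On size, SAP 4 plans 15 per arm and says: "This is a Phase I study and is not intended to be powered for the primary endpoint".

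**The concern.** The test named as the primary analysis covers part of its endpoint. A participant with one mild event and a participant with a severe or serious event contribute the same count.

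This matters because AE incidence could well be similar in the two arms. Participants must already have at least two respiratory symptoms scored two or higher. Protocol 8.1 counts any undesired occurrence as an AE, whether or not it is related to study drug. The window is four weeks. If most participants in both arms report something, a difference in harm would lie mainly in grade and seriousness, which the test does not see.

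The contradiction adds a second problem. A reader of SAP 5.1 expects a p-value, while a reader of SAP 8.2 or Protocol 9.4.1 expects none. Whether the test is reported should not be open to choice once data are unblinded.

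**Working it through.** The documents give no AE rate, effect size, power or alpha for this endpoint, so there is no figure of the plan to reproduce. The check asks what the test can and cannot detect.

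**Inputs.** From the SAP: 15 per arm (Section 4), two-sided alternative, chi-square or Fisher (Section 5.1). Assumed: alpha 0.05, the rate read as participants with at least one AE, and all event counts and rates below.

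**1. Pure shift in grade.** Let k of 15 participants in each arm have an AE, all severe on Ampion and all mild on placebo.

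- The table for the SAP 5.1 test is k v k. The observed difference is 0, so Fisher and chi-square both give p = 1.00 for every k.
- For severe AEs the table is k v 0, and two-sided Fisher is p = 2 × C(15,k) / C(30,k).

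| k per arm | SAP 5.1 test | Fisher, severe AEs (k v 0) | Wilcoxon, worst grade |
|---|---|---|---|
| 3 | 1.00 | 2 × 455/4,060 = 0.224 | 0.81 |
| 5 | 1.00 | 2 × 3,003/142,506 = 0.042 | 0.55 |
| 6 | 1.00 | 2 × 5,005/593,775 = 0.017 | 0.41 |
| 9 | 1.00 | 0.0007 | 0.077 |
| 12 | 1.00 | 0.00001 | 0.001 |

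**2. Rejection rate when incidence is equal.** Summing binomial probabilities over all 16 × 16 outcomes, with 60% or 80% of participants in both arms having an AE, Fisher rejects 1.6–1.7% of the time and uncorrected chi-square 4.9–5.0%. Grade is not an input, so these figures are the same with no effect and with a complete mild-to-severe shift.

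**3. Why a worst-grade rank test is not a full substitute.** At k = 6, the chance that an Ampion participant has a worse grade than a placebo participant, counting ties as half, is 6/15 + ½ × (9/15) × (9/15) = 0.40 + 0.18 = 0.58. That is close to 0.50 because most participants tie at no event, hence p = 0.41.

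In a second profile, 60% of each arm has an AE, split mild/moderate/severe as 50/10/0% on placebo and 5/15/40% on Ampion. By simulation the rank test rejects about 35%. Fisher on severe AEs needs at least 5 v 0, so its power is P(X ≥ 5) for X ~ Bin(15, 0.40), which is 78%.

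**4. What 15 per arm can support.** With no severe events on placebo, 5 of 15 on Ampion are needed for p ≤ 0.05. Exact Fisher power is 28% for 30% v 5% and 52% for 40% v 5%. For a milder shift, with severe AEs at 20% v 5% and equal overall incidence, the worst-grade test rejects only about 9–16%, depending on the profile.

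Interval widths say the same. At 40% in both arms the approximate 95% half-width for a difference is 1.96 × √(2 × 0.40 × 0.60 / 15) = 0.35. At 20% v 5% it is 1.96 × √((0.20 × 0.80 + 0.05 × 0.95) / 15) = 0.23.

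**The case against.** The strongest reply is that severity is compared between arms, only not tested. SAP 8 summarises AEs by arm and severity, and Tables 10.3.2 and 10.3.3 cover the primary window. This stands. A reader might infer that SAP 5.1 is the only between-arm analysis of the endpoint, or that a mild-to-severe shift would go unseen. The documents do not support either reading, because such a shift would show in those tables. What holds is narrower: the only specified test, to which SAP 8.2 points as the primary analysis, cannot reflect it.

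A second reply is that if SAP 8.2 and Protocol 9.4.1 govern, there is no test and the by-arm tables are the primary analysis. That is largely right, and it is why reconciliation comes first. It would still leave SAP 5.1 to be rewritten, and the severe-AE and SAE comparisons without a difference or interval.

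A third reply is that the trial is openly unpowered, and the SAP does not say that a non-significant result will be reported as no difference. Protocol 6.1 and 3.5 also give severe reactions and SAEs their own DSMB review. All of this stands. It would be too strong to say that the trial cannot answer its safety question or that severe harm has no route to attention.

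Finally, a reader might conclude that a Wilcoxon test on worst grade should replace the present test. The working does not support that: it can be much less sensitive than the severe-AE comparison, and it does not capture seriousness, which Protocol 8.2 defines separately from grade.

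**Conclusion.** The point holds in this form. The single hypothesis test specified for the primary endpoint uses an undefined AE rate, omits the severity and SAE components that the endpoint names, and conflicts with two statements that AEs will not be tested. That its p-value does not change under a pure shift in grade follows from its construction and needs no assumed rates, only the reading of the rate as participants with any AE.

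The rejection rates and p-values are illustrations. They rest on assumed AE profiles, several of them extreme, and on an assumed two-sided 0.05. At this sample size no choice of test gives good power for moderate differences, so the gain is an analysis that matches its endpoint rather than one that reliably detects harm. This should be corrected before unblinding, but it does not undermine the trial.

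**What to change.** 1. Reconcile SAP 5.1 with SAP 8.2 and Protocol 9.4.1, so that all three say either that a test will be done or that the primary analysis is descriptive. With 15 per arm, estimation is the more informative choice.
2. Define the AE rate in SAP 5.1 as the proportion of participants with at least one AE from baseline to Day 28. State the denominator, and whether all AEs or only treatment-emergent AEs count, since Table 10.3.2 uses the latter.
3. Make the primary analysis the by-arm participant proportions with (a) any AE, (b) at least one severe AE and (c) at least one SAE. Give each with the between-arm difference and a 95% CI by a method suited to small samples and zero counts.
4. Beside these, show the by-arm distribution of worst grade: none, mild, moderate, severe. Because SAP 6.3 assigns the greatest severity when data are missing, footnote how many grades were assigned that way.
5. An ordinal worst-grade summary may be added as support, but not as the sole replacement.

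The cost is one rewritten paragraph in SAP 5.1, an aligned sentence in SAP 8.2 (and in Protocol 9.4.1 if a test is kept), and a few rows in Tables 10.3.2 and 10.3.3. Severity and seriousness are already recorded for every AE, so no new data are needed. The downside is a longer table with wide intervals.
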